1.10 Timing of outcome assessments and recording of nutritional intake

All outcome assessments are based upon data from the index hospitalization. Daily nutrition intake was assessed only for up to a maximum of 28 days in the ICU. This included daily enteral formula type and volume, daily enteral caloric and protein intake, and daily intravenous fat (as propofol) and glucose calories administered.

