Intercurrent events: Subjects may be missing transthyretin due to death, discharge from the hospital, or recovery. Those participants who die will have a transthyretin level equal to the lowest value observed amongst the surviving subjects. Participants who are discharged alive

from the hospital before the primary outcome is measured will have a transthyretin level set equal to the highest observed measure. Multiple imputation will be used to account for study participants who did not have transthyretin measured in the expected window.

Summary measure: The difference in mean transthyretin levels between treatment arms.

5. Study Population

The investigation will enroll 500 subjects using the following inclusion and exclusion criteria:

Inclusion: critically ill adult trauma patients who are started on enteral nutrition within 72 hours of admission to the intensive care unit and are expected to require nutritional support for at least 1 week. Non-trauma post-surgical patients meeting study entry criteria will be included as well. This is expected to include patients recovering from emergency surgery, including amputations, debridement of necrotizing soft-tissue infections, and other serious surgical illnesses.

Exclusion: An individual who meets *any* of the following criteria will be excluded from participation in this study:

- Significant chronic organ failure,
- severe malnutrition,
- not expected to survive due to severity of injuries and,
- serum creatinine >2 mg/dl.

6. Data sources

Data will be collected concurrently with study subject enrollment and treatment in the intensive care unit. extracted from the electronic medical record.

7. Outcomes

7.1 Primary endpoint:

Circulating transthyretin concentrations measured 14 – 21 days after injury.

7.2 Secondary endpoint:

- Ventilator free days: the numbers of days on which the subject does not require assisted ventilation during the first 28 days following the date of injury. VFD will be set to zero for all participants who die before hospital discharge.
- Hospital acquired pneumonia: Pneumonia diagnosed while the patient is in the hospital. Pneumonia will be defined as the presence of a positive quantitative culture from a bronchoalveolar lavage sample coupled with the use of antibiotics.

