7.3 Subgroups for primary endpoint

- NUTRIC score (< 5 vs ≥ 5),
- CRP (> 100 vs ≤ 100),

- CRP (> 100 vs ≤ 100) at day 14 (or closest measurement) in those participants in the ICU at least 7 days,
- Trauma patients only.

7.5 Exploratory outcomes:

- ICU-free days in the first 28 days after injury. ICU-free days will be set to zero for those participants who die before hospital discharge.
- Death before hospital discharge.
- Time to hospital discharge alive.
- Pneumonia from the trauma registry for trauma patients.

7.6 Safety outcomes:

- Select adverse events, including gastrointestinal intolerance and possible aspiration.
- Dialysis.
- Blood urea nitrogen.
- Serum creatinine.

8. Statistical Methodology

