8.12.1 Multiple Imputation

Twenty complete imputed datasets will be created using linear regression. The multiple imputation model will be performed within each treatment group for those who survive hospital discharge, and within deaths separately. Covariates will include age, sex, race/ethnicity, NUTRIC score, ventilator free days, and previous values of transthyretin when available. For each complete dataset, the differences in means between treatment groups as well as the standard error of that difference will be calculated; these results will be combined across imputations using Rubin's rule.²

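### SAP 4 gives the highest transthyretin to everyone discharged alive before measurement, whatever the destination, so a hospice discharge or a ventilated transfer gets the recovery score

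*SAP*

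**What the plan says.** The primary endpoint in SAP 7.1 is "Circulating transthyretin concentrations measured 14 – 21 days after injury". SAP 4 names death, discharge and recovery as separate reasons why it may be missing, and then gives three rules:

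- Participants who die "will have a transthyretin level equal to the lowest value observed amongst the surviving subjects".
- Participants discharged alive "from the hospital before the primary outcome is measured will have a transthyretin level set equal to the highest observed measure".
- For the rest, "Multiple imputation will be used to account for study participants who did not have transthyretin measured in the expected window".

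The summary measure is a difference in means, so the assigned extremes enter at full weight.

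Neither document mentions hospice, transfer to another facility, or discharge disposition. Protocol 1.10 adds that "All outcome assessments are based upon data from the index hospitalization", so nothing is seen after a participant leaves.

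Other sections describe missing values differently. SAP 8.12 and 9 list death among the reasons for imputing, and SAP 8.12.1 runs the imputation "within each treatment group for those who survive hospital discharge, and within deaths separately". None of these sections adds a condition on destination.

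**The concern.** The highest value makes sense as a score for recovery. SAP 9 points the same way: it links high transthyretin to patients who are well enough to have it. The rule in SAP 4, however, is triggered by leaving alive, which is broader than recovering. It also covers a patient who leaves to die elsewhere and a patient moved to another facility while still on a ventilator or tube feeding. Such a patient gets the best score in the trial, while a similar patient who stays and dies gets the worst.

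The entry exclusion for people not expected to survive does not prevent this, because it is applied at enrollment and not to later decline. The planned sensitivity analyses are not described as reaching it either. The tipping-point shift in SAP 8.12.2 acts on imputed values, the alternative is last observation carried forward, and neither varies the score by destination.

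At stake is the primary comparison. If one arm had more of these discharges, the rule would raise that arm's mean transthyretin and make worse outcomes look like benefit.

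**Working it through.** **The plan's own figure.** Inputs from SAP 9: 500 participants (250 per arm at 1:1), difference 2.4 mg/dl, SD 7.0, two-sided alpha 0.05, and 25% of patients with no effect.

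- Diluted difference = 0.75 × 2.4 = 1.8 mg/dl.
- Standard error = 7.0 × √(2/250) = 0.626 mg/dl.
- Power = Φ(1.8/0.626 − 1.96) = Φ(0.915) = 82%.

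This agrees with the stated 80%, so the sample size is not in dispute. The 0.626 serves below as a yardstick.

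**Shift from an imbalance.** Let d be the difference between arms in the share of unfavourable live discharges before measurement, M the highest observed value, and A the value such a patient would otherwise get.

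Shift in the mean difference = d × (M − A)

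The documents give none of these three, so all are assumptions:

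- M: about 300 measured values with the plan's mean of 12 and SD of 7 have an expected maximum of about 32 if normal and about 42 if right-skewed (gamma).
- A: 12, the plan's control mean, for a dependent transfer; 1 to 5, an assumed lowest value, for a hospice discharge scored as a death. (The gamma minimum is about 1.)
- d: 1 percentage point, which is 2.5 patients in an arm of 250.

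| A (mg/dl) | M = 32 | M = 42 |
|---|---|---|
| 12 | 0.01 × 20 = 0.20 | 0.01 × 30 = 0.30 |
| 5 | 0.01 × 27 = 0.27 | 0.01 × 37 = 0.37 |
| 1 | 0.01 × 31 = 0.31 | 0.01 × 41 = 0.41 |

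One percentage point therefore moves the estimate by 0.20 to 0.41 mg/dl, which is 0.32 to 0.65 of the planned standard error. The shift is proportional to d.

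**Equal numbers in both arms.** The expected shift is then about zero and the cost is variance. If a share p is moved from a typical value of 12 to M, the variance is (1 − p) × 49 + p(1 − p)(M − 12)². With p = 2% (assumed):

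- M = 32: 48.02 + 0.0196 × 400 = 55.9, SD 7.5.
- M = 42: 48.02 + 0.0196 × 900 = 65.7, SD 8.1.

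Those figures start from the plan's SD of 7. Once deaths and other early discharges already sit at the extremes (assumed 8% deaths and 10% to 30% early live discharges), the composite SD is larger and a further 2% at the maximum raises it by only about 1% to 5%.

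**The case against.** The strongest objection is that the SAP may not use the fixed values at all: SAP 8.12, 8.12.1 and 9 describe imputation where SAP 4 assigns extremes. If imputation governs, the problem disappears. The conflict is real and has to be settled, but SAP 4 is where the estimand is defined, and its rule is faulty as stated.

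The second objection is size. The counts are unknown, entry criteria make very early hospice discharge less likely, and chance imbalance is already covered by the standard error. Under the composite scoring with the death and discharge shares assumed above, that standard error is about 0.84 to 1.40, larger than 0.63. All of this stands. Systematic bias needs a treatment-related imbalance, which the documents do not show.

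Third, changing the primary score now is not neutral. Protocol 3.4 reports arm differences in respiratory events from initial analyses, followed by record reviews from January to April 2023; the SAP is dated August 2023. That also stands, and it is why the rule as now written should be reported too.

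A reader might also draw three stronger conclusions, which the documents do not support:

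- *Ventilator-free and ICU-free days are mis-scored for transferred patients.* SAP 7.2 defines a ventilator-free day by the need for assisted ventilation, not by whether the day was observed. SAP 8.7 and 8.9 impute missing outcomes for these endpoints, and Protocol 1.7 imputes ventilator-free days after loss to follow-up. The rule that "VFD will be set to zero for all participants who die before hospital discharge" does not turn unobserved ventilated days into free ones.
- *Hospice discharges should count as deaths on every endpoint.* Death before discharge and "Time to hospital discharge alive" (SAP 7.5) are clear in-hospital endpoints. Recoding them would change what they measure.
- *The rule favours the supplemental arm.* Protocol 3.4 reports more reintubation and possible aspiration there, but nothing links those events to hospice or dependent discharge.

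**Conclusion.** The concern holds for the primary endpoint. The highest-value rule in SAP 4 depends only on leaving alive before transthyretin is measured, and no other section restricts it to recovery. Participants discharged to hospice or transferred while dependent are scored at the wrong end of the scale.

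The size cannot be determined from the documents. On the assumed maxima and alternative values, each percentage point of imbalance is worth roughly 0.2 to 0.4 mg/dl against a diluted planning effect of 1.8, so an imbalance of a few points would matter and none would cost only precision. The SAP also does not say whether a transfer to another hospital is a discharge; on its plain wording, with follow-up limited to the index stay, it is. This should be corrected, but it is not evidence that the result is biased.

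**What to change.** Amend SAP 4 to use discharge disposition from the electronic record:

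1. Give the highest value only to participants discharged before measurement because they recovered, meaning off ventilation and off enteral nutrition, whatever the receiving facility.
2. Give hospice discharges before measurement the same transthyretin score as deaths.
3. Send other dependent transfers to the multiple imputation already planned.
4. State that this rule governs, and align SAP 8.12, 8.12.1 and 9 with it.
5. Because arm-level data were seen before the SAP date, report the rule as it now stands in SAP 4 alongside, as a sensitivity analysis.

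For ventilator-free and ICU-free days, only confirm that unobserved days after a ventilated or ICU-level transfer count as missing under SAP 8.7 and 8.9. Leave in-hospital death and time to live discharge as defined.

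The cost is one variable from a source already in use, some SAP wording and one extra analysis. The downside is that a few more primary values are imputed; how many depends on disposition counts that the documents do not give.

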7.3 Subgroups for primary endpoint

- NUTRIC score (< 5 vs ≥ 5),
- CRP (> 100 vs ≤ 100),

- CRP (> 100 vs ≤ 100) at day 14 (or closest measurement) in those participants in the ICU at least 7 days,
- Trauma patients only.

7.5 Exploratory outcomes:

- ICU-free days in the first 28 days after injury. ICU-free days will be set to zero for those participants who die before hospital discharge.
- Death before hospital discharge.
- Time to hospital discharge alive.
- Pneumonia from the trauma registry for trauma patients.

7.6 Safety outcomes:

- Select adverse events, including gastrointestinal intolerance and possible aspiration.
- Dialysis.
- Blood urea nitrogen.
- Serum creatinine.

8. Statistical Methodology

8.1 Randomization

Participating patients were randomized to high (an additional 2 g/kg/day) vs. standard protein levels in a ratio of 1:1.

8.4 Intent to Treat (ITT) Analysis

All efficacy analysis will be conducted under the ITT principle. Patients will be included in the study arm according to the treatment group to which they were randomly assigned. All randomized subjects will be included in these analyses.

8.5 Primary Statistical Hypothesis

The null hypothesis is that the mean circulating transthyretin level, measured between days 14 and 21, in the group of subjects randomized to the intervention arm is equal to the mean in the control group.

8.6 Primary Analysis

A t-test with unequal variances will be used to test the primary hypothesis. The analysis will use 20 imputed data sets, with results combined across imputations.

8.7 Secondary Analysis

Analyses of the VFD endpoint will be based on the intent-to-treat principle using imputed data if there is missing outcome data. The mean VFD for the increased protein group will be compared to the mean within the control group using a t-test allowing for unequal variances.

The number and proportion of participants diagnosed with hospital acquired pneumonia will be summarized. The proportion will be compared between treatment arms using a score-based test.

8.8 Subgroup Analyses

The primary analysis will be repeated in subgroups defined by:

- mNUTRIC score (<5 vs ≥ 5),
- CRP (> 100 vs ≤ 100),
- CRP (> 100 vs ≤ 100) at day 14 (+/-) in those participants in the ICU at least 7 days; and,
- Trauma patients only.

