1.11 Confidence intervals and p-values

95% confidence will be presented for selected key outcomes. P-values will be two-sided without adjustment for multiplicity. We will use the traditional two-sided $p \leq 0.05$ to indicate statistical significance for the primary and other prespecified outcomes. For subgroup analyses we will report only confidence intervals.

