With 500 participants this study has 80% power to detect a difference of 2.4 mg/dl in average circulating transthyretin levels during the third week between the protein supplementation group (assumed average circulating transthyretin level of 14.4, and the standard of care group (assumed average circulating transthyretin level of 12.0, with a pooled standard deviation of 7.0). This conservatively assumes that there will be 25% of the patients for whom the protein supplementation has no effect in that they are either well enough to have high circulating transthyretin levels or die prior to obtaining the primary outcome. Because the primary outcome is a surrogate marker, we do not plan for any formal interim analyses to evaluate efficacy or futility. Safety of our intervention will be reviewed by an independent Data Safety Monitoring Board (DSMB) on a regular basis. Currently, the Harborview Medical Center typically admits about 300 - 350 trauma victims per year who would meet eligibility criteria. With enrollment over 4 - 5 years, we anticipate that ~1500 patients will be eligible. Therefore, the rate of recruitment among eligible patients needs to be ~33%. The statistical analysis of the primary hypothesis will use a two-sided t-test with alpha of 0.05. We expect that less than 10% of patients will die prior to day 21. For these and for patients who are lost-to-follow-up prior to day 21, we will multiply impute the primary outcome separately for each group and incorporate previously observed circulating transthyretin levels (if available) and patient age information as well as sex, race/ethnicity, NUTRIC score, and ventilator free days.

10. Statistical and Data Programming

All data cleaning and programming will be done in either the statistical software R (R Foundation) or in SAS (SAS).

References (for this document: Statistical Design and Power)

2. Rubin DB. *Multiple imputation for nonresponse in surveys*. Wiley series in probability and mathematical statistics Applied probability and statistics,. Wiley; 1987:xxix, 258 pages.

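### SAP 8.8 gives an estimate within each subgroup but never estimates the difference in effect between subgroups

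*SAP*

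**What the plan says.** SAP 8.8: "The primary analysis will be repeated in subgroups defined by" mNUTRIC score (below 5 or not), CRP (above 100 or not), CRP at about day 14 among patients with at least seven days in intensive care, and trauma patients. SAP 7.3 has the same list. Its last item reads "Trauma patients only", and no non-trauma group is listed, although SAP sections 4 and 5 admit non-trauma surgical patients. The analysis being repeated is the unequal-variance t-test on 20 imputed datasets (SAP 8.6).

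Protocol 1.11 adds: "For subgroup analyses we will report only confidence intervals". SAP 8.11 has a similar intervals-only rule, but it names exploratory and safety analyses and does not mention subgroups.

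Neither document plans a treatment-by-subgroup term, a contrast between subgroups, or a rule for reading the subgroup results. The one planned interaction is treatment by study day, in the GEE model of SAP 8.9.

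**The concern.** A subgroup analysis asks whether the treatment effect differs between kinds of patient. Separate estimates do not answer that. One interval may exclude zero and the other include it while the two effects are equal, simply because each subgroup is smaller than the trial and its power is moderate. Without a contrast in the report, readers will tend to compare the intervals by eye. At stake is a false impression that supplemental protein raises transthyretin only in, say, high-NUTRIC or high-CRP patients.

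**Working it through.** **Inputs.** All are from SAP section 9 except the 1:1 allocation (SAP 8.1).
- Size and power: "With 500 participants this study has 80% power to detect a difference of 2.4 mg/dl", so 250 per arm.
- Test: "The statistical analysis of the primary hypothesis will use a two-sided t-test with alpha of 0.05".
- SD: "with a pooled standard deviation of 7.0".
- Dilution: "there will be 25% of the patients for whom the protein supplementation has no effect", so the average effect is 0.75 × 2.4 = 1.8 mg/dl.
- Subgroup sizes are not given, so every split below is an assumption. The SD is taken as 7.0 in each subgroup, and extra variance from imputation is ignored.

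**Step 1: reproduce the stated power.** SE = 7.0 × √(2/250) = 0.626. Power = Φ(1.8/0.626 − 1.96) = Φ(0.915) = 0.82, close to the stated 80%. Other readings fit less well: 2.4 with 250 per arm gives 0.970, 2.4 with 187.5 per arm gives 0.913, and 1.8 with 187.5 per arm gives 0.702. The diluted effect of 1.8 is therefore taken as the design value.

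**Step 2: power in one half.** With 125 per arm, SE = 7.0 × √(2/125) = 0.885. Power = Φ(1.8/0.885 − 1.96) = Φ(0.073) = 0.529.

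**Step 3: chance that exactly one interval excludes zero.** For two independent complementary subgroups with powers p1 and p2 and the same true effect, this is p1(1 − p2) + p2(1 − p1). For equal halves: 2 × 0.529 × 0.471 = 0.498.

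**Step 4: vary the effect and the split.**

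| Common true effect (mg/dl) | Split | Power in each subgroup | Exactly one excludes zero |
|---|---|---|---|
| 1.8 | 50/50 | 0.529, 0.529 | 0.498 |
| 1.8 | 70/30 | 0.672, 0.350 | 0.552 |
| 1.8 | 90/10 | 0.779, 0.147 | 0.697 |
| 2.4 | 50/50 | 0.774, 0.774 | 0.350 |
| 2.4 | 90/10 | 0.953, 0.227 | 0.747 |
| 1.0 | 50/50 | 0.203, 0.203 | 0.324 |
| 0 | any | 0.05, 0.05 | 0.095 |

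**Step 5: the direct contrast.** If the effect is uniform, a 95% CI for the difference between the two subgroup effects excludes zero about 5% of the time. A simulation of 40,000 trials with equal halves gave 5.0% at 1.8 mg/dl and 5.2% at 2.4. The same runs gave 50.0% and 35.5% for the discordance in step 3.

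**Step 6: precision of the contrast.** SE = 0.626 × √(1/f + 1/(1 − f)), where f is the share of patients in one subgroup. At f = 0.5 the SE is 1.25 and the 95% half-width is 1.96 × 1.25 = 2.45 mg/dl. At 70/30 the half-width is 2.68, and at 80/20 it is 3.07.

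**The case against.** A reader might infer that the plan judges subgroups by whether the primary test is significant in each one. The documents do not support that. Protocol 1.11 reserves the significance threshold for the primary and other prespecified outcomes and gives subgroups intervals only. Neither document states a subgroup hypothesis, decision rule or claim. Taken together they plan estimation, and the harm arises only if readers use the intervals as tests. This stands. What remains is that a 95% interval excludes zero exactly when the two-sided test gives p < 0.05, so an intervals-only rule does not by itself prevent the misreading.

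A reader might also infer that a uniform effect will look like a subgroup difference half the time whatever the circumstances. That too is unsupported, because the true effect and the splits are unknown and the figure moves widely with both.

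For the trauma item, the discordance figure is undefined because no complement is listed. The item can also be read as a restriction to the core population, since the SAP's estimand puts trauma patients first and then adds surgical patients. That reading is fair, but any statement that trauma patients respond differently would still need the non-trauma estimate.

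For NUTRIC and CRP, a careful reader could compute the difference from the two reported intervals. This is true and lowers the severity, but the analysts can do it more reliably.

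Finally, the contrast is weak: its half-width of 2.45 mg/dl exceeds the 1.8 mg/dl design effect, so it will seldom settle the question. This also stands, and it is a reason to show the contrast, because separate intervals hide that limit.

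**Conclusion.** The point holds as a minor one. The plan never estimates whether the effect differs by subgroup, and neither document says how the separate intervals should be read. For two complementary subgroups with a uniform effect of 1.8 mg/dl, SD 7.0 and an assumed 50/50 split, comparing intervals against zero gives an apparent difference about 50% of the time. Over the other effects and splits examined, the figure runs from about 10% to 75%. Every value exceeds the roughly 5% of a direct contrast. The primary test, its alpha and its power are unaffected.

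**What to change.** In SAP 8.8:

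1. For NUTRIC, CRP and trauma versus non-trauma, report the treatment-by-subgroup difference with its 95% CI beside the subgroup estimates, and include the non-trauma estimate. First confirm that the first CRP item is a baseline value; SAP 7.3 and 8.8 give no time for it.
2. Add CRP and trauma status to the imputation model used for these analyses. SAP 8.12.1 includes NUTRIC but neither of these. Imputing within arm without them tends to pull their contrasts toward zero, by an amount that depends on how much is imputed.
3. Repeat the intervals-only rule of Protocol 1.11, and state that any claim of a differing effect rests on the contrast.
4. State that the contrast is imprecise (half-width about 2.45 mg/dl at 50/50 and 3.07 at 80/20), so an interval that includes zero does not show equal effects.
5. Keep the day-14 CRP subgroup out of these contrasts. It is defined by a value and a length of stay that arise after randomization and may be affected by treatment.

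Protocol 3.4 describes analyses by arm before record reviews held in January to April 2023, and the SAP is dated August 20, 2023. The added contrast should therefore carry its own date.

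The cost is one contrast per factor and an imputation rerun for the subgroup analyses, with no new data collection.
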